7.3. Efficacy

7.3.1. Exploratory Biomarker(s)/Pharmacodynamic Markers

With the subject's consent, blood samples will be collected at the time points indicated in the Time and Events Table (Section 7.1) to investigate pharmacodynamic response to GSK3196165 and will be analyzed pre- and post-GSK3196165. In addition blood samples will be collected and may be analyzed for markers which may be predictive of lung damage. The timing of the collections may be adjusted on the basis of emerging PK, pharmacodynamic or safety data from this study or other new information in order to ensure optimal evaluation of the pharmacodynamic endpoints. Details on the blood sample collection, processing, storage and shipping procedures are provided in the Central Laboratory Manual. All samples may be retained for a maximum of 15 years after the last subject completes the study. Results of biomarker studies may be reported separately from the main clinical study report, and additional exploratory analyses may be performed to further characterize novel biomarkers.

7.3.2. Biomarkers

Pharmacodynamic biomarkers may include, but not limited to, the following:

- Target engagement (TE): analysis of free soluble GM-CSF and soluble GM-CSF complexed to GSK3196165.
- Effects of GSK3196165 on target cell populations: may include, but not limited to, circulating levels of T, B, NK, Th17, T regulatory cells and activated monocytes, dendritic cells, neutrophils.
- Biomarkers which may be indicative of RA disease activity: may include, but not limited to 14-3-3η, ACPA, CRP, and RF.
- Soluble biomarkers which may be predictive of response to GSK3196165 such as C1M, C2M, C3M, CRPM, VICM, MRP8/14, MMP-3, and 14-3-3η.
- Pharmacodynamic biomarkers to assess response to GSK3196165 such as IL-1β, TNFα, IL-6, IL-8, IL15, IL-23 and IL-17A/F, and chemokines such as CCL17, CXCL4, CXCL7, CXCL13, CCL22; and complement proteins such as C5a, ratio C3/C3dg, TCC, C4, C4a, sCD163.
- Biomarkers of extracellular matrix (ECM) or aggrecan degradation (e.g. may include, but not limited to, YKL 40, ARGS neoepitope).

Additional exploratory biomarkers in the blood/serum (RNA, DNA, protein) may include but will not be limited to the following:

- Whole blood RNA markers of GM-CSF/macrophage signaling and response to GSK3196165.
- Whole blood DNA analysis to explore the relationship between genetic variants in the host and response to GSK3196165.

Safety biomarkers which may be predictive of lung damage including, but not limited to, the following:

- Analysis of KL 6, SAA, SP-D, cholestenoic acid, and measurement of GM-CSF autoantibodies at baseline.
- These will be analyzed at the end of the study or in the event of a pulmonary safety signal which would require further investigation.

7.3.3. Target Engagement (TE)

If data permits, a PK/TE modeling analysis will be conducted. This modeling work will be detailed in the reporting and analysis plan (RAP).

The rationale for the selection of timepoints is:

- Baseline: to measure PK and target engagement (± potential biomarkers status) at baseline.
- Week 1 and Week 2: to characterize the increase in PK and target engagement (± activation of potential biomarkers) due to the loading phase.
- Week 4: to measure target engagement (± biomarkers) at the maximum plasma concentration.
- Week 6 and Week 8: to measure if a maintenance regimen administered every two weeks can maintain sufficient target engagement (± activation of potential biomarkers) at steady state.
- Week 12 and Week 22: to assess the decline in PK and target engagement after the last dose.

7.4. Novel Biomarkers

With the subject's consent, blood sample(s) will be collected during this study and may be used for the purposes of measuring novel biomarkers to identify factors that may influence RA, and/or medically related conditions, as well as the biological and clinical responses to GSK3196165. If relevant, this approach will be extended to include the identification of biomarkers associated with AEs.

Evaluation of a range of exploratory novel biomarkers will allow confirmation of target engagement and expected pharmacologic effects. These data may also allow hypotheses to be generated with respect to subgroups that are most likely to benefit from GSK3196165 treatment or early on-treatment biomarkers that may predict subsequent response/remission (or lack of response/remission), that may guide Phase III development and ultimately treatment guidelines for prescribers.

Performance of these investigations may be conditional on the results of the clinical trial principally, but not exclusively, on the primary measures of the clinical trial outcome and samples may be selected for analysis on the basis of the clinical outcome. Unless stated otherwise, these investigations may be performed irrespective of whether a response to GSK3196165 is observed.

Comparative examination of pre-dosing profiles of participants may uncover known or novel candidate biomarkers/profiles which could be used to predict response to treatment

with GSK3196165 or provide new insights into RA and medically related conditions. Comparative examination of post-dosing profiles in conjunction with pre-dosing profiles may yield known and novel candidate biomarkers/profiles and new insights which relate to the action of GSK3196165. All samples will be retained for a maximum of 15 years after the last subject completes the trial.

Details on the blood sample collection, processing, storage and shipping procedures are provided in the Central Laboratory Manual.

Novel candidate biomarkers and subsequently discovered biomarkers of the biological response associated with RA or medically related conditions and/or the action of GSK3196165 may be identified by application of:

- RNA analysis of blood samples.
- Measurement of the levels of a subset of RNA species on blood samples.

7.5. Clinical Efficacy

7.5.1. Magnetic Resonance Imaging

The most affected hand will be documented at screening and used for all imaging visits. If subjects report both hands are equally involved, then the subject's dominant hand will be used. Each subject's most affected hand/wrist will be imaged by MRI at Screening, Week 4, Week 12 and Week 22 (see Section 7.1, Time and Events Schedule). The scanning protocol will include routine localizers, T1 measurement sequences, dynamic DCE-MRI acquisition, and acquisitions required for OMERACT RAMRIS and RAMRIQ scoring.

The following will be assessed:

- Change from baseline in synovitis, osteitis and erosion as assessed OMERACT RAMRIS and RAMRIQ in the hand/wrist.
- Change from baseline in joint inflammation as measured by DCE-MRI in the hand/wrist:
 - K^{trans}.
 - V_{e.}
 - V_{p.}
 - IRE.
 - ME.

7.5.2. Clinical assessments

Efficacy assessments will be performed at the time points presented in the Time and Events Table (Section 7.1).

Efficacy assessments will include evaluation of all 68 joints for tenderness and 66 joints for swelling to be performed by an independent joint evaluator, visual analogue scale (VAS) (global disease) for the subject and treating physician, HAQ-DI – physical

function, which includes an item on pain severity in the past week, as well as other health outcome measures described in more detail in Section 7.11 and laboratory assessments (CRP). Based on these assessments ACR (20, 50 and 70), DAS28(CRP) and the EULAR response will be calculated.

RA symptoms will be assessed through the subject completion of an RA Symptom and Impact Diary (see Section 7.11.2).

7.5.3. Joint Assessments

The procedure for joint assessments can be found in the SRM.

7.5.3.1. Replaced or Fused Joints

Replaced or fused joint will not be included in joint evaluations. The reason for absence of the evaluations of those joints must be recorded.

7.5.3.2. Independent Joint Evaluator

One or more independent assessors, who have documented experience in performing joint assessments, will be designated at each study site to perform joint assessments. Preferably the same independent assessor will perform all joint assessment for the same subject throughout the study. The principal investigator must ensure that the independent joint assessor has documented experience and he/she is adhering to locally accepted and implemented standards. This also applies if the independent joint assessor is replaced during the study.

The independent joint assessor should have no other contact with the subject during the study, must not be the treating physician (investigator), should not discuss the subject's clinical status with the subject during the joint assessment nor with other site personnel, and will not be permitted to review the subject's medical records, the eCRF, nor any of the previous joint assessments.

7.5.4. Patient's Assessment of Arthritis Pain

Subjects will assess the severity of their current arthritis pain using a 100 unit VAS by placing a mark on the scale between "0" (no pain) and "100" (most severe pain), which corresponds to the magnitude of their pain.

Further details of this assessment are provided in the SRM.

7.5.5. Patient's Global Assessment of Arthritis

Subjects will complete a global assessment of disease activity using the PtGA item, a VAS with anchors "0" (very well) to "100" (very poor).

Further details of this assessment are provided in the SRM.

7.5.6. Physician's Global Assessment of Arthritis

Physicians will complete a global assessment of disease activity using the PhGA, a VAS with anchors "0" (none) to "100" (extremely active), respectively.

Further details of this assessment are provided in the SRM.

7.5.7. DAS Assessments

The disease activity score (DAS) assessment is a derived measurement with differential weighting given to each component. The DAS 28(CRP) or DAS 28(ESR) will be calculated at each assessment time point.

The components of the DAS28 arthritis assessment include:

- Tender/Painful Joint Count (28).
- Swollen Joint Count (28).
- CRP or ESR.
- PtGA.

7.5.8. ACR Assessments

The ACR's definition for calculating improvement in RA (ACR20) is calculated as a 20% improvement in tender and swollen joint counts and 20% improvement in 3 of the 5 remaining ACR-core set measures: patient and physician global assessments, pain, disability, and an acute-phase reactant. Similarly, ACR50 and 70 are calculated with the respective percent improvement. This efficacy measurement will be made at every study assessment time point.

The specific components of the ACR Assessments that will be used in this study are:

- Tender/Painful Joint count (68).
- Swollen Joint Count (66).
- Patient's Assessment of Arthritis Pain.
- PtGA.
- PhGA.
- CRP or ESR.
- HAQ-DI.

7.6. Safety

Planned time points for all safety assessments are listed in the Time and Events Table (Section 7.1).

7.6.1. Screening Visits

- Chest X-ray (posterior to anterior [PA] and lateral, or in accordance with local requirements).
 - If a chest X-ray has been taken within the past 12 weeks that shows no clinically-significant abnormality, and there are no signs or symptoms suggestive of pulmonary disease that would exclude the subject, then a further chest X-ray is not required.
- Baseline chest HRCT for subjects with D_{LCO} values $\geq 60\%$ <70%, and it is recommended that the subject will be reviewed by a local pulmonologist to exclude significant pre-existing respiratory disease.
- Immunogenicity testing.

7.6.2. Study Visits

Subjects will have systematic safety monitoring throughout the study. Additional time points for safety tests (such as vital signs, physical exams and laboratory safety tests) may be added during the course of the study based on newly available data to ensure appropriate safety monitoring.

In addition to routine laboratory assessments, ECG monitoring, and evaluation of AEs, particular attention will be paid to respiratory events and function given the potential risk associated with targeting GM-CSF and the effects on alveolar macrophages. This may result in the occurrence of the extremely rare condition of PAP, which is characterized by the accumulation of surfactant lipids and protein in the alveolar spaces (with no fibrosis), with resultant impairment in gas exchange, which may lead to increase a risk of secondary pulmonary infections.

All subjects will return for a follow-up visit at 12 weeks after last dose of study medication.

7.6.3. Safety Endpoints and Other Assessments

- Incidence of AEs/SAEs.
- Incidence of serious infections and opportunistic infections.
- Pulmonary events (cough, dyspnea, pulse oximetry, spirometry, D_{LCO}).
- Lung biomarkers (such as SP-D, KL-6, lactate dehydrogenase [LDH], cholestenoic acid).
- ECG measurements.
- Vital signs.
- Hematological and clinical chemistry parameters.
- Physical examinations.
- Pregnancy test (for women of child-bearing potential).

7.6.4. Adverse Events (AE) and Serious Adverse Events (SAEs)

The definitions of an AE or SAE can be found in Appendix 12.4.

The investigator and their designees are responsible for detecting, documenting and reporting events that meet the definition of an AE or SAE.

7.6.4.1. Time Period and Frequency for Collecting AE and SAE Information

AEs and SAEs will be collected from the start of study treatment until the follow-up contact (12 weeks after the last dose of study medication), at the time points specified in the Time and Events Table (Section 7.1).

Medical occurrences that begin prior to the start of study treatment but after obtaining informed consent may be recorded on the Medical History/Current Medical Conditions section of the eCRF.

Any SAEs assessed as related to study participation (*e.g.*, protocol-mandated procedures, invasive tests, or change in existing therapy) or related to a GSK product will be recorded from the time a subject consents to participate in the study up to and including any follow-up contact.

All SAEs will be recorded and reported to GSK within 24 hours, as indicated in Appendix 12.4.

Investigators are not obligated to actively seek AEs or SAEs in former study subjects. However, if the investigator learns of any SAE, including a death, at any time after a subject has been discharged from the study, and he/she considers the event reasonably related to the study treatment or study participation, the investigator must promptly notify GSK.

NOTE: The method of recording, evaluating and assessing causality of AEs and SAEs plus procedures for completing and transmitting SAE reports to GSK are provided in Appendix 12.4.

7.6.4.2. Method of Detecting AEs and SAEs

Care will be taken not to introduce bias when detecting AEs and/or SAEs. Open-ended and non-leading verbal questioning of the subject is the preferred method to inquire about AE occurrence. Appropriate questions include:

- "How are you feeling?"
- "Have you had any (other) medical problems since your last visit/contact?"
- "Have you taken any new medicines, other than those provided in this study, since your last visit/contact

7.6.4.3. Follow-up of AEs and SAEs

After the initial AE/SAE report, the investigator is required to proactively follow each subject at subsequent visits/contacts. All SAEs, and non-serious AEs of special interest (as defined in Section 4.6.1) will be followed until resolution, until the condition stabilizes, until the event is otherwise explained, or until the subject is lost to follow-up (as defined in Section 5.4). Further information on follow-up procedures is given in Appendix 12.4.

7.6.4.4. Cardiovascular and Death Events

For any cardiovascular (CV) events detailed in Appendix 12.4 and all deaths, whether or not they are considered SAEs, specific CV and Death sections of the eCRF will be required to be completed. These sections include questions regarding CV (including sudden cardiac death) and non-cardiovascular death.

The CV eCRFs are presented as queries in response to reporting of certain CV Medical Dictionary for Regulatory Activities (MedDRA) terms. The CV information should be recorded in the specific CV section of the CRF within 1 week of receipt of a CV event data query prompting its completion.

The Death eCRF is provided immediately after the occurrence or outcome of death is reported. Initial and follow-up reports regarding death must be completed within 1 week of when the death is reported.

Investigators will be required to fill out event specific data collection tools for CV AEs and SAEs detailed in Section 12.4.4, Appendix 12.4. This information should be recorded in the specific cardiovascular eCRF within 1 week of when the AE/SAE(s) are first reported.

7.6.5. Laboratory and Other Safety Assessment Abnormalities Reported as AEs and SAEs

Any abnormal laboratory test results (hematology, clinical chemistry, or urinalysis) or other safety assessments (*e.g.*, ECGs, radiological scans, vital signs measurements), including those that worsen from baseline, and felt to be clinically significant in the medical and scientific judgment of the investigator are to be recorded as AEs or SAEs.

However, any clinically significant safety assessments that are associated with the underlying disease, unless judged by the investigator to be more severe than expected for the subject's condition, are not to be reported as AEs or SAEs.

7.6.6. Adverse Events of Special Interest

Please see Section 4.6.1 for a discussion of potential risks with GSK3196165. AEs of special interest include:

- Serious infections, including serious respiratory infections and TB.
- Opportunistic infections.

- Neutropenia (grade 3 or 4).
- Respiratory events including:
 - Persistent (for 3 consecutive weeks) reduction in D_{LCO} >15%
 - Persistent (for 3 consecutive weeks) cough and/or dyspnea
 - Non-life-threatening pulmonary changes related to surfactant accumulation.
- PAP.
- Hypersensitivity reactions, including anaphylaxis.
- Injection site reactions.
- Persistent cough or dyspnea.

7.6.6.1. Disease-Related Events and/or Disease-Related Outcomes Not Qualifying as SAEs

The following have been specified as disease-related events (DREs) for the study:

- Events related to exacerbation of articular/peri-articular manifestations of RA, will not be reported as AEs, and will be recorded in the DRE eCRF.
- Events related to the articular/peri-articular flare up of the disease, and that requires hospitalization, will not be reported as SAEs. However, such events must still be recorded in the DRE eCRF.

These DREs will be monitored by an SRT on a routine basis.

NOTE: However, if either of the following conditions apply, then the event must be recorded and reported as an SAE (instead of a DRE):

• The event is, in the investigator's opinion, of greater intensity, frequency, or duration than expected for the individual subject.

OR

• The investigator considers that there is a reasonable possibility that the event was related to treatment with the investigational product.

New onset or worsening of extra-articular manifestations of RA should be reported as AEs/SAEs.

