12.4.1. Definition of Adverse Events

Adverse Event Definition:

- An AE is any untoward medical occurrence in a patient or clinical investigation subject, temporally associated with the use of a medicinal product, whether or not considered related to the medicinal product.
- NOTE: An AE can therefore be any unfavorable and unintended sign (including an abnormal laboratory finding), symptom, or disease (new or exacerbated) temporally associated with the use of a medicinal product.

Events meeting AE definition include:

- Any abnormal laboratory test results (hematology, clinical chemistry, or urinalysis) or other safety assessments (*e.g.*, ECGs, radiological scans, vital signs measurements), including those that worsen from baseline, and felt to be clinically significant in the medical and scientific judgment of the investigator.
- Exacerbation of a chronic or intermittent pre-existing condition including either an increase in frequency and/or intensity of the condition.
- New conditions detected or diagnosed after study treatment administration even though it may have been present prior to the start of the study.
- Signs, symptoms, or the clinical sequelae of a suspected interaction.
- Signs, symptoms, or the clinical sequelae of a suspected overdose of either study treatment or a concomitant medication (overdose per se will not be reported as an AE/SAE unless this is an intentional overdose taken with possible suicidal/self-harming intent. This should be reported regardless of sequelae).
- "Lack of efficacy" or "failure of expected pharmacological action" per se will not be reported as an AE or SAE. However, the signs and symptoms and/or clinical sequelae resulting from lack of efficacy will be reported if they fulfil the definition of an AE or SAE.

Events **NOT** meeting definition of an AE include:

- Any clinically significant abnormal laboratory findings or other abnormal safety assessments which are associated with the underlying disease, unless judged by the investigator to be more severe than expected for the subject's condition.
- Signs and symptoms of RA disease activity, *e.g.* joint pain, swelling, erythema, warmth, and stiffness, or expected progression, should not be reported as AEs, unless

in the investigator's opinion they are of greater intensity, frequency or duration than expected for the individual subject.

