12.4.6. Evaluating AEs and SAEs

Assessment of Intensity

The investigator will make an assessment of intensity for each AE and SAE reported during the study and will assign it to one of the following categories:

- Mild: An event that is easily tolerated by the subject, causing minimal discomfort and not interfering with everyday activities.
- Moderate: An event that is sufficiently discomforting to interfere with normal everyday activities.
- Severe: An event that prevents normal everyday activities. An AE that is assessed as severe will not be confused with an SAE. Severity is a category utilized for rating the intensity of an event; and both AEs and SAEs can be assessed as severe.
- An event is defined as 'serious' when it meets at least one of the pre-defined outcomes as described in the definition of an SAE.

Assessment of Causality

- The investigator is obligated to assess the relationship between study treatment and the occurrence of each AE/SAE.
- A "reasonable possibility" is meant to convey that there are facts/evidence or arguments to suggest a causal relationship, rather than a relationship cannot be ruled out.
- The investigator will use clinical judgment to determine the relationship.
- Alternative causes, such as natural history of the underlying diseases, concomitant therapy, other risk factors, and the temporal relationship of the event to the study treatment will be considered and investigated.
- The investigator will also consult the IB (GSK Document Number 2014N190256_01) and/or Product Information, for marketed products, in the determination of his/her assessment.
- For each AE/SAE the investigator must document in the medical notes that he/she

has reviewed the AE/SAE and has provided an assessment of causality.

- There may be situations when an SAE has occurred and the investigator has minimal information to include in the initial report to GSK. However, it is very important that the investigator always make an assessment of causality for every event prior to the initial transmission of the SAE data to GSK.
- The investigator may change his/her opinion of causality in light of follow-up information, amending the SAE data collection tool accordingly.
- The causality assessment is one of the criteria used when determining regulatory reporting requirements.

Follow-up of AEs and SAEs

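### Section 7.6.6.1 makes an RA flare an SAE without any seriousness test, which contradicts Appendix 12.4 and can inflate SAE incidence or make it inconsistent between sites

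*Protocol*

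**What the plan says.** Section 7.6.6.1 defines two kinds of DRE. The first has no seriousness element: "Events related to exacerbation of articular/peri-articular manifestations of RA, will not be reported as AEs, and will be recorded in the DRE eCRF". The second is an articular flare "and that requires hospitalization, will not be reported as SAEs". A NOTE after both bullets reverses the exemption: "if either of the following conditions apply, then the event must be recorded and reported as an SAE (instead of a DRE"). The conditions, each left to the investigator's opinion, are that the event is "of greater intensity, frequency, or duration than expected for the individual subject", or that "there is a reasonable possibility that the event was related to treatment with the investigational product".

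Appendix 12.4, which section 7.6.4 names as the place where AE and SAE are defined, says something different:

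- Appendix 12.4.1 lists RA signs and symptoms among events that are not AEs: joint pain, swelling, erythema, "warmth, and stiffness, or expected progression, should not be reported as AEs, unless" they exceed what the investigator expected for that subject. This is the NOTE's first condition, but the result is an AE. Possible relation to study drug is not an exception here.
- Appendix 12.4.2 says that an event outside the AE definition cannot be an SAE, even if a serious outcome occurs, and then lists the serious outcomes.
- Appendix 12.4.6 calls an event serious "when it meets at least one of the pre-defined outcomes as described in the definition of an SAE", and warns against confusing severity with seriousness.

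Sections 1 and 3 list the incidence of AEs and of SAEs as secondary endpoints.

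**The concern.** The NOTE uses intensity and causality as if they were seriousness. A site that follows it must file an SAE for an outpatient flare that exceeded expectation, or for an ordinary flare that the investigator thinks could be drug-related. A site that works from Appendix 12.4 files an AE for the former and nothing for the latter.

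SAE incidence would then depend partly on which section a site applied, and it would include events with no serious outcome. There are operational effects too. SAE status starts 24-hour reporting (section 7.6.4.1), and section 6.4 lets the sponsor's safety staff unblind any subject with an SAE. Neither seems intended for a non-serious flare.

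**Working it through.** The plan gives no figure to reproduce. The check is a comparison of the two rules, followed by one line of arithmetic for scale.

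**Comparison.** Each type of articular flare is classified first under section 7.6.6.1 as written, then under Appendix 12.4 as written. Expected and above expectation refer to the individual subject. The outpatient rows assume that no other serious outcome is met.

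| Flare | Section 7.6.6.1 | Appendix 12.4 | Agree? |
|---|---|---|---|
| Outpatient, expected, not related | DRE | Not an AE | Yes |
| Outpatient, above expectation | SAE | AE, not serious | No |
| Outpatient, expected, possibly related | SAE | Not an AE, so cannot be an SAE | No |
| Hospitalized, expected, not related | DRE | Not an AE, so cannot be an SAE | Yes |
| Hospitalized, above expectation | SAE | AE with a listed outcome: SAE | Yes |
| Hospitalized, expected, possibly related | SAE | Not an AE, so cannot be an SAE | No |

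The rules disagree in three of the six rows. In the two outpatient rows the NOTE produces an SAE with no serious outcome. In the last row the outcome is serious, but Appendix 12.4.1 lacks the relatedness condition, so Appendix 12.4.2 blocks SAE status. A change to the NOTE alone would leave Appendix 12.4.1 in conflict with it wherever the flare is possibly related but of expected intensity.

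The general list in Appendix 12.4.1 does count exacerbation of a pre-existing condition as an AE. The bullet on RA signs is the more specific text, however, and it takes expected RA activity back out.

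**Scale.** Planned arm sizes are 30 on GSK3196165 and 10 on placebo (section 9.2.1). Incidence is taken as the proportion of subjects with at least one SAE. One extra subject, with no other SAE, who is counted because of a non-serious flare adds:

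- GSK3196165: 1/30 = 0.033, about 3.3 percentage points
- Placebo: 1/10 = 0.10, or 10 percentage points

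These are steps per subject, not per flare. Two flares in one placebo subject still give 1/10 = 10 points; flares in two placebo subjects give 2/10 = 20 points.

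The contrast between 3.3 and 10 comes only from the 3:1 allocation. If a subject has the same probability p of being added in each arm, the expected rise is 30p/30 = p on GSK3196165 and 10p/10 = p on placebo.

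**The case against.** The best defence is a narrower reading. The title of section 7.6.6.1 concerns events that do not qualify as SAEs, and its only explicit exemption from SAE reporting is for hospitalized flares. The NOTE may have been meant only to restore SAE status to those. That may be the intent, but the NOTE refers to the event without limitation and follows a bullet that does not require hospitalization. The narrower reading also leaves the last row of the table unresolved.

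The clause in Appendix 12.4.2 on important medical events allows some non-hospitalized flares to be judged serious. It calls for judgment case by case and does not support an automatic SAE.

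Over-reporting is cautious for the individual subject, the safety review team already monitors DREs, and section 7.6.6.2 already asks for prompt notice of non-serious related AEs. These points reduce the practical harm. They do not make the incidence figure consistent.

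The synopsis calls all endpoints exploratory and section 9.1 plans no formal hypothesis tests. This stands, and it limits the consequence to the description of safety.

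A reader might infer that the rule flatters the active arm, because flares should be commoner on placebo plus methotrexate with no DMARD or biologic rescue. The documents do not support this. They give no flare rate by arm, and the relatedness condition can apply in either arm. Section 6.10.2.1 allows limited intra-articular corticosteroid for severe flares, and section 4.5.2 lets the investigator withdraw a subject for unacceptable disease activity. A reader might also infer that any extra stiffness becomes an SAE. It does not: the threshold is what was expected for that subject, so an expected flare with no suspected relation to study drug stays a DRE.

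**Conclusion.** The contradiction is real and rests on the text alone. Section 7.6.6.1 makes SAE reporting mandatory on grounds that Appendix 12.4 does not accept as seriousness, and in the relatedness case for events that Appendix 12.4 excludes from AEs altogether.

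SAE incidence can be inflated, and inconsistent between sites, to the extent that sites follow the NOTE literally. The effect is about 3.3 points per affected subject on GSK3196165 and 10 points on placebo, assuming the planned arm sizes, incidence counted by subject, and no other SAE in that subject. How many subjects would be affected, and whether one arm would be affected more, cannot be derived from the documents.

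The point concerns a secondary safety endpoint and does not threaten the primary biomarker objective. It should be corrected because the error is clear and the correction is small.

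**What to change.** Make two edits together:

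1. In the NOTE of section 7.6.6.1, keep both conditions but change the result: the event is recorded as an AE instead of a DRE, and as an SAE only if it also meets a seriousness criterion in Appendix 12.4.2.
2. In the RA bullet of Appendix 12.4.1, add possible relation to the investigational product as a second exception beside the above-expectation one.

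Applied to the table, the two outpatient flares in dispute become AEs. Hospitalized flares meeting either condition are SAEs under both sections, and flares meeting neither condition stay DREs. All six rows then agree.

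The cost is about two sentences in a protocol amendment and a line of site guidance. No new data are collected.
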